## 7.5 Causality Assessment of Adverse Events

For all AEs, the Principal Investigator will provide an assessment of causal relationship to the study treatment (active or placebo). The causality assessment must be recorded in the subject's source documents and on the AE eCRF. Causal relationship will be classified according to the following criteria:

1. *Unrelated*: The event is clearly due to causes other than the active study drug.
2. *Unlikely*: The event is doubtfully related to active study drug. The event was most likely related to other factors such as the subject's clinical state, concomitant drugs or other therapeutic interventions.
3. *Possible*: The event follows a reasonable temporal sequence from the time of active study drug administration but could have been produced by other factors such as the subject's clinical state, therapeutic interventions or concomitant drugs.
4. *Probable*: The event follows a reasonable temporal sequence from the time of active study drug administration and follows a known response pattern to the drug. The toxicity cannot be reasonably explained by other factors such as the subject's clinical state, therapeutic interventions or concomitant drugs.
5. *Definite*: The event follows a reasonable temporal sequence from the time of active study drug administration, follows a known response pattern to the drug, cannot be reasonably explained by other factors such as the subject's condition, concomitant drugs or therapeutic interventions, AND either occurs immediately following active study drug administration, improves on stopping the study drug, or reappears on re-exposure.

## 7.6 Adverse Event Severity Assessment

The severity of each AE will be graded according to the NCI CTCAE, version 4.03. The severity of AEs that are not specifically listed in the CTCAE will be categorized according to the general guidelines provided in the CTCAE, and as summarized in the table below.

**Table 3. General Guidelines for Severity Assessment of Adverse Events**

Grade 1 : Mild; asymptomatic or mild symptoms; clinical or diagnostic observations only; intervention not indicated.
Grade 2 : Moderate; minimal, local or noninvasive intervention indicated; limiting age-appropriate instrumental activities of daily living (ADL) [preparing meals, shopping for groceries or clothes, using the telephone, managing money, etc.].
Grade 3 : Severe or medically significant but not immediately life-threatening; hospitalization or prolongation of hospitalization indicated; disabling; limiting self-care ADL (bathing, dressing and undressing, feeding self, using the toilet, taking medications, and not bedridden).
Grade 4 : Life-threatening consequences; urgent intervention indicated.
Grade 5 : Death related to AE.

Note the distinction between the severity and the seriousness of an AE. A severe AE is not necessarily a SAE. For example, a headache may be severe (interferes significantly with subject's usual function) but would not be classified as serious unless it met one of the criteria for SAEs, listed above in [Section 7.3](#).

## 7.7 Expectedness of Adverse Event

An unexpected AE is defined in 21 CFR 312.32(a) as follows:

An AE is considered “unexpected” if it is not listed in the IB or is not listed at the specificity or severity that has been observed; or, if an IB is not required or available, is not consistent with the risk information described in the general investigational plan or elsewhere in the current application, as amended.

## 7.8 Assessment of Adverse Event Outcome

Outcome of AEs will be defined according to International Council for Harmonisation (ICH) Topic E2B, ICH Guideline.

- **Recovered/Resolved:** The subject has recovered fully from the AE without any remaining effects or impairment.
- **Recovered/Resolved with Sequelae:** The subject has recovered, but with an after effect possibly due to disease or treatment.
- **Not Recovered/Not Resolved:** The condition is still present.
- **Fatal:** Fatal should only be used when death is possibly related to the AE.
- **Unknown:** The primary outcome is not known at the time of the final assessment. If an outcome for an AE is not available at the time of the initial report, follow-up will proceed until an outcome is known or followed up to the Final Study Visit. Any subject with a possible study treatment-related AE at the Final Study Visit will be followed until resolution or stabilization of the event. Further, any SAE, whether or not related to Study treatment (active or placebo), that occurs within 30 days following the last dose of Study treatment will be followed until resolution or stabilization of the event.

## 7.9 Clinical Findings

Any significant clinical findings at Visit 3 will be followed until the condition returns to pre-study status, stabilizes, or can be explained as not being study treatment related. If the clinical finding is reported as an AE (per the criteria outlined in [Section 7.4](#)), the follow-up procedures for AEs defined above will apply.

## 8 STATISTICAL METHODS

This section describes the statistical methods to be used for the analysis and reporting of data collected under Protocol No. ORA-D-018. Additional details will be provided in the statistical analysis plan.

### 8.1 Study Design

The primary analysis is a comparison of difference in endogenous glucose production for the ORMD-0801 treated group and placebo. Let  $pC$  be the endogenous glucose production for the control (placebo) arm and let  $pT$  be the endogenous glucose production for the treatment (ORMD-0801) arm. The primary analysis is:

$$H_0 : pC = pT$$

$$H_1 : pC \neq pT$$

Trial success is defined as having the endogenous glucose production for the placebo group being greater than the endogenous glucose production for the ORMD-0801 treated group.

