
### 3 INVESTIGATIONAL PLAN

#### 3.1 Overall Study Design and Plan

This study is designed to explore the efficacy of ORMD-0801 compared to placebo on endogenous glucose production in subjects with type 2 diabetes (T2DM). Subjects will undergo an initial Screening Visit (Visit 0) to establish their eligibility to participate in the study. At Visit 1 (2 weeks after the Screening Visit), qualifying subjects will be randomized to either ORMD-0801 (8 mg) or matching placebo, study medication will be dispensed and subjects will dose, twice a day, once in the morning prior to breakfast and once at night prior to bedtime. Doses will occur at 45 minutes ( $\pm$  15 minutes) before breakfast and no later than 10 AM each morning, and at 8 PM ( $\pm$  120 minutes) each night, and no sooner than 1 hour after dinner. Subjects will return to the clinic, 2 weeks later, for Visit 2. At this visit, subject compliance will be assessed, medication will be dispensed, a blood sample will be collected to measure HbA1c and subjects will be questioned for any adverse events. Subjects will be scheduled to return to the clinic in 2 weeks for morning admission (8 AM  $\pm$  120 minutes) to the PK unit (Visit 3). Subjects will be provided with standardized meals and the morning dose in-clinic. A light standardized dinner meal will be provided at 6 PM  $\pm$  30 minutes. At approximately 8 PM ( $\pm$  60 minutes, and no sooner than 1 hour after dinner), subjects will be dosed with their study medication and will be started on a 16-hour infusion of [6,6-H2]-glucose tracer. Blood samples will be collected to measure endogenous glucose (tracer attached), plasma glucose, metabolites and hormones for the duration of the infusion. Blood samples will be drawn at baseline (pre-infusion), 45, 90, 120 and 150 minutes, and 3, 4, 5, 6, 7, 8, 9, 10, 11, 12, 13, 14, 15 and 16 hours (see [Table 2](#) for blood draw schedule). Subjects will be required to remain fasting from the evening of Day 28 until the end of the infusion. Water intake will be unrestricted. On Day 29, blood sample will also be collected to measure HbA1c. Following completion of the infusion, the subjects will receive a standardized lunch and will be observed for an additional 6 hours. Prior to discharge, a physical examination will be performed, and blood/urine samples will be collected for safety chemistry, hematology and urinalysis, following which subjects will be discharged from the CRU and will exit the study.

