## 5.2 Randomization

This is a randomized, double blind, parallel study. Approximately 40 subjects with T2D will be randomized to one of two treatment groups.

Integrium, LLC will generate and implement the randomization procedures for this trial. A computer-generated randomization schedule will be used for assigning the treatment groups. The Investigational Site pharmacist will follow this randomization schedule to dispense the appropriate study treatment.

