### 8.2 Sample Size

Sample size determination was not based on statistical considerations.

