### 8.3 Primary Efficacy Evaluation

The primary endpoint for this study is the difference in endogenous glucose production between active and placebo as measured by the glucose with tracer attached using  $AUC_{(0-16)}$ .

The primary endpoint will be analyzed using an Analysis of Variance model with treatment as the main effect.

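### Section 8.1 defines trial success by direction alone, without rejection of H0 or any alpha; read literally, an inert drug succeeds half the time

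*Combined protocol and SAP*

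**What the plan says.** Section 8.1 defines pC and pT as endogenous glucose production (EGP) in the placebo and ORMD-0801 arms and sets H0: pC = pT against the two-sided H1: pC ≠ pT. It then adds: "Trial success is defined as having the endogenous glucose production for the placebo group being greater than the endogenous glucose production" for the group given ORMD-0801.

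Section 8.3 names the model for AUC(0-16): "The primary endpoint will be analyzed using an Analysis of Variance model with treatment as the main effect". It attaches no significance level or decision rule. The Statistical Methods entry in the synopsis gives none either.

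Three other statements bear on the point:
- Section 8 opens by deferring detail: "Additional details will be provided in the statistical analysis plan".
- Section 8.2 says of the sample size: "Sample size determination was not based on statistical considerations".
- Section 3.1 describes the aim as exploratory: "This study is designed to explore the efficacy of ORMD-0801 compared to placebo on endogenous glucose production".

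**The concern.** The success sentence is worded as a definition, and its only condition is which arm has the higher EGP. It mentions no rejection of H0, p-value, confidence limit or margin. The two-sided H1 above it cannot supply the missing condition, because H1 would be met equally if the drug raised EGP.

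The plan can therefore declare success when its own primary test does not reject. In a trial of about 40 subjects whose size has no statistical basis, a favourable difference that falls short of significance is a likely result, and that is where the two readings part. Nothing in the supplied text prevents the reading, or the alpha, from being settled after the data are seen. Section 12.4 commits to making negative and inconclusive results public, but Section 8.1 gives no workable way to tell those from success.

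**Working it through.** The plan states no alpha, power, effect size or SD, so it has no figure of its own to reproduce. The check compares the rule as written with the rule probably intended.

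**Inputs**
- Total sample size, Section 5.2: "Approximately 40 subjects with T2D will be randomized to one of two treatment groups".
- Allocation ratio: not stated. Section 5.2 says only "A computer-generated randomization schedule will be used for assigning the treatment groups". Assumed 1:1, so n = 20 per arm.
- Model: ANOVA with treatment as the only effect. With two arms this is the pooled two-sample t-test, with 20 + 20 − 2 = 38 degrees of freedom.
- Alpha: not stated. Assumed two-sided 0.05, with 0.10 as a second case.
- Data: assumed normal. The effect d is the true placebo-minus-active difference in SD units; a positive d means the drug lowers EGP.

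**Formulas**
- Standard error of the observed standardised difference: √(2/20) = 0.316.
- Literal rule: P(placebo mean > active mean) = Φ(d / 0.316).
- Rejection rule: P(T > t critical), where T is noncentral t with 38 df and noncentrality d / 0.316.

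**Results**

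| True effect d | Literal rule | Reject at 0.05, placebo higher | Reject at 0.10, placebo higher |
|---|---|---|---|
| −0.2 (drug raises EGP) | 0.264 | 0.005 | – |
| 0 (inert) | 0.500 | 0.025 | 0.050 |
| 0.2 | 0.736 | 0.090 | – |
| 0.5 | 0.943 | 0.338 | 0.463 |
| 0.8 | 0.994 | 0.693 | 0.799 |

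A simulation of 200,000 trials at each of d = 0, 0.2, 0.5 and 0.8 agreed within 0.002 (literal 0.501, 0.737, 0.943, 0.995; rejection at 0.05: 0.025, 0.089, 0.337, 0.692).

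**Where the two rules disagree**
- Smallest observed difference that rejects: t(0.975, 38) × 0.316 = 0.640 SD at alpha 0.05, and t(0.95, 38) × 0.316 = 0.533 SD at alpha 0.10. Any observed advantage between 0 and 0.64 SD is a success by the sentence and a non-rejection by the test at 0.05.
- Inert drug: 0.500 − 0.025 = 0.475 of trials fall in that gap.
- True 0.5 SD reduction: 0.943 − 0.338 = 0.605 of trials do.

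**How far the 50% depends on assumptions**
- It needs no SD, effect size or alpha. It is exact for normal data at any allocation, and for any continuous distribution at equal allocation, because under no effect the two arms are exchangeable.
- With skewed data (lognormal, log-SD 0.5) and unequal arms, simulation gave 49.6% at 18:22, 48.8% at 13:27 and 47.9% at 10:30.

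**The case against.** The strongest reply is that the success sentence follows directly after H0 and H1 and uses the same two quantities. It can be read as naming which direction of a two-sided rejection counts as a win, which is a usual way to pair a two-sided test with a directional claim. On that reading an inert drug does not succeed half the time. A bare comparison of means would also leave the hypotheses and the ANOVA with no part in the decision. This is a fair account of the likely intent, and the 50% belongs to the literal reading only. It does not rescue the rule: the link to rejection is unstated, and even if it is implied there is no alpha to apply. At 0.10 instead of 0.05, false success doubles from 2.5% to 5%, and success at a true 0.5 SD reduction moves from 34% to 46%.

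A second reply is that Section 8 defers detail to the statistical analysis plan, where an alpha would normally sit. A plan finalised before unblinding could supply it, and the documents do not say when that happens, so a post hoc choice is possible rather than shown. The supplied text nonetheless contains no such rule. The success definition itself is not deferred, so a rejection requirement added only in the SAP would change what the protocol says.

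Third, the study is exploratory, no go/no-go decision in the text depends on the word success, and the planned model is the same under either reading. That limits the weight of the point. It also makes deleting the sentence a reasonable remedy.

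**Conclusion.** The concern holds, and the sentence is wrong as written. Followed literally, it gives an inert drug a 50% chance of success and a drug that raises EGP by 0.2 SD a 26% chance, against 2.5% and 0.5% if rejection at two-sided 0.05 were required. The 50% follows from symmetry alone. The other figures rest on an assumed 20 per arm, normal data and an assumed alpha. The absence of any alpha is a defect under either reading. This should be fixed, but in an exploratory study of this size it affects the label put on the result rather than the analysis performed.

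**What to change.** Replace the success sentence in Section 8.1 with wording such as:

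> Trial success is defined as rejection of H0 in the primary AUC(0-16) model at two-sided alpha = [value fixed before unblinding, for example 0.05], with estimated mean EGP lower for ORMD-0801 than for placebo. The difference will be reported with its 100(1 − alpha)% confidence interval.

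The 0.05 is an example, since the documents give no level. Tying the interval to the chosen alpha keeps interval and test from disagreeing. Under the normal model, false success for an inert drug is then alpha/2, or 2.5% at 0.05.

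If the study is meant to be purely exploratory, delete the success sentence and report the estimated difference with its 95% confidence interval.

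Either change is one sentence in Section 8.1, matched in the SAP, with no operational effect. The first sets a much stricter bar than the literal rule, as the table shows: at the assumed 20 per arm, even a true 0.8 SD reduction succeeds in only about 69% of trials at alpha 0.05. The second avoids that bar but gives up any formal claim of success.

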### 8.2 Sample Size

Sample size determination was not based on statistical considerations.

### 8.3 Primary Efficacy Evaluation

The primary endpoint for this study is the difference in endogenous glucose production between active and placebo as measured by the glucose with tracer attached using  $AUC_{(0-16)}$ .

The primary endpoint will be analyzed using an Analysis of Variance model with treatment as the main effect.

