Study Design	This study is designed to explore the efficacy of ORMD-0801 compared to placebo on endogenous glucose production in subjects with type 2 diabetes (T2DM). Subjects will undergo an initial Screening Visit (Visit 0) to establish their eligibility to participate in the study. At Visit 1 (2 weeks after the Screening Visit), qualifying subjects will be randomized to either ORMD-0801 (8 mg) or matching placebo, study medication will be dispensed and subjects will dose twice a day, once in the morning prior to breakfast and once at night prior to bedtime. Doses will occur at 45 minutes ( $\pm$ 15 minutes) before breakfast and no later than 10 AM each morning, and at 8 PM ( $\pm$ 120 minutes) each night, and no sooner than 1 hour after dinner. Subjects will return to the clinic, 2 weeks later, for Visit 2. At this visit, subject compliance will be assessed, medication will be dispensed, a blood sample will be collected to measure HbA1c and subjects will be questioned for any adverse events. Subjects will be scheduled to return to the clinic in 2 weeks for morning admission (8 AM $\pm$ 120 minutes) to the PK unit (Visit 3). Subjects will be provided with standardized meals and the morning dose in-clinic. A light standardized dinner meal will be provided at 6 PM $\pm$ 30 minutes. At approximately 8 PM ( $\pm$ 60 minutes, and no sooner than 1 hour after dinner), subjects will be dosed with their study medication and will be started on a 16-hour infusion of [6,6- $^2$ H 2 ]-glucose tracer. Blood samples will be collected to measure endogenous glucose (tracer attached), plasma glucose, metabolites and hormones for the duration of the infusion. Blood samples will be drawn at baseline (pre-infusion), 45, 90, 120 and 150 minutes, and 3, 4, 5, 6, 7, 8, 9, 10, 11, 12, 13, 14, 15 and 16 hours. Subjects will be required to remain fasting from the evening of Day 28 until the end of the infusion. Water intake will be unrestricted. On Day 29, blood sample will also be collected to measure HbA1c. Following completion of the infusion, the subjects will receive a standardized lunch and will be observed for an additional 6 hours. Prior to discharge, a physical examination will be performed, and blood/urine samples will be collected for safety chemistry, hematology and urinalysis, following which subjects will be discharged from the CRU and will exit the study.

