Primary Endpoint	1. Difference in endogenous glucose production between active and placebo as measured by the glucose with tracer attached using AUC (0-16) as the primary parameter.

Secondary Endpoints	

1. Mean changes in HbA1c from baseline to Day 29 of the treatment period.

2. Mean changes plasma glucose levels from baseline to Day 29 of the treatment period.

3. Mean changes in ketones from baseline to Day 29 of the treatment period.

4. Mean Changes in FFA from baseline to Day 29 of the treatment period.

5. Mean change in TC, LDLC, HDLC and TG from baseline to Day 29 of the treatment period.

6a. Difference in endogenous glucose production between active and placebo as measured by the glucose with tracer attached using other parameters including, but not limited to:

a. AUC(0-2), AUC(0-4), AUC(0-8), AUC(0-12),

b. AUC(2-16), AUC(4-16), AUC(8-16), AUC(12-16),

c. Cmax,

d. Tmax, and

e. Tlag.

6b. Difference in metabolites (<math>\beta</math>-hydroxybutyrate, acetoacetate, lactate, pyruvate, FFA, glycerol) and hormones (insulin, C-peptide, glucagon) between active and placebo using the same AUC intervals as endogenous glucose production.

7. Safety assessed by adverse event reporting including adverse events of special significance such as hypoglycemia.

Duration of Participation	Subjects will be evaluated for participation in the study during a 1 to 3-week Screening period. Following Screening, eligible subjects will enter a 4-week double blind treatment period.

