## 1 INTRODUCTION

Endogenous insulin – secreted by the  $\beta$ -cells of the endocrine pancreas – flows to the liver in the portal blood before reaching the systemic circulation through the hepatic veins. Following oral administration, the insulin in ORMD-0801 is absorbed through the gastrointestinal mucosa into the mesenteric veins (mostly, the superior mesenteric vein that drains blood from the jejunum and ileum) and reaches the liver *via* the portal vein, thereby mimicking the route of entry of endogenous insulin. The main action of insulin in the liver is to suppress glucose production; for this action, sensitivity is higher, and onset and offset time of this action are faster than for insulin stimulation of glucose uptake by peripheral tissues. First-pass extraction of insulin by the liver is 50-60%; recirculation raises this percentage to ~80%. As a consequence, portal plasma insulin concentrations normally are ~3-fold higher than peripheral insulin levels.

The hypothesis behind ORMD-0801 is that sufficient oral insulin survives gastrointestinal degradation to arrive at the liver where it inhibits glucose production and, through this effect, lowers fasting plasma glucose concentrations. As the majority of this exogenous insulin dose is degraded in the liver, the resulting systemic insulin levels may be only marginally increased, thereby avoiding the risk of hypoglycemia.

The use of glucose tracers is the standard non-invasive approach to measure endogenous glucose production (EGP). A tracer (in this protocol, [6,6-H2]-glucose, a stable isotope of glucose) infused intravenously at a constant rate will equilibrate with endogenous glucose across its distribution space within ~3 hours. From this time onward, the ratio of the tracer infusion rate to the plasma tracer/tracee ratio (as assayed by GCMS) measures EGP. As compared to placebo, oral insulin is expected to reduce EGP over the ensuing 13 hours of continued fasting. In patients with type 2 diabetes, EGP is known to be abnormally elevated and to contribute the hyperglycemia. Oral insulin is therefore addressing a key pathophysiological derangement of type 2 diabetes.

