## 2 STUDY OBJECTIVES AND ENDPOINTS

Objectives	Endpoints
Primary Objective: 

1. To assess the differences in endogenous glucose production in subjects with type 2 diabetes treated for 4 weeks either with ORMD-0801 or matching placebo following an intravenous infusion of [6,6-2H2]-glucose tracer using AUC(0-last).

	Primary Endpoint: 

1. Difference in endogenous glucose production between active and placebo as measured by the glucose with tracer attached using AUC(0-16) as the primary parameter.

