Secondary Objectives: 

1. To compare the change from baseline in HbA1c levels measured at Week 4 in type 2 diabetic patients treated for 4 weeks with either ORMD-0801 or matching placebo.

2. To compare the change from baseline in plasma glucose levels measured at Week 4 in type 2 diabetic patients treated for 4 weeks with either ORMD-0801 or matching placebo.

3. To compare the change from baseline in ketone levels measured at Week 4 in type 2 diabetics treated for 4 weeks with either ORMD-0801 or matching placebo.

4. To compare the change from baseline in FFAs measured at Week 4 in type 2 diabetics treated for 4 weeks with either ORMD-0801 or matching placebo.

5. To compare the change from baseline in TC, LDLC, HDLC, and TG measured at Week 4 in type 2 diabetics treated for 4 weeks with either ORMD-0801 or matching placebo.

6. To assess the differences in endogenous glucose production in patients with type 2 diabetes treated for 4 weeks either with ORMD-0801 or matching placebo following an intravenous infusion of [6,6-2H2]-glucose tracer using other parameters including, but not limited to, Cmax, Tmax, Tlag and AUC over different time intervals.

7. To assess the safety of repeat administration of ORMD-0801 in patients with type 2 diabetes inadequately controlled on oral therapy.

	Secondary Endpoints: 

1. Mean changes in HbA1c from baseline to Day 29 of the treatment period.

2. Mean changes plasma glucose levels from baseline to Day 29 of the treatment period.

3. Mean changes in ketones from baseline to Day 29 of the treatment period.

4. Mean Changes in FFA from baseline to Day 29 of the treatment period.

5. Mean change in TC, LDLC, HDLC and TG from baseline to Day 29 of the treatment period.

6a. Difference in endogenous glucose production between active and placebo as measured by the glucose with tracer attached using other parameters including, but not limited to:

a. AUC(0-2), AUC(0-4), AUC(0-8), AUC(0-12),

b. AUC(2-16), AUC(4-16), AUC(8-16), AUC(12-16),

c. Cmax,

d. Tmax, and

e. Tlag.

6b. Difference in metabolites (β-hydroxybutyrate, acetoacetate, lactate, pyruvate, FFA, glycerol) and hormones (insulin, C-peptide, glucagon) between active and placebo using the same AUC intervals as endogenous glucose production.

7. Safety assessed by adverse event reporting including adverse events of special significance such as hypoglycemia.

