## 6.2 Efficacy Assessments

### 6.2.1 16-Hour Tracer Infusion

A 16-hour tracer infusion will be performed after 28 days of treatment. The blood draw schedule during the tracer infusion is documented in [Table 2](#) in [Section 3.7](#) of the protocol. Based on the blood draws the values for the following lab tests will be obtained:

- Endogenous Glucose Production (glucose that is produced by the liver which has the tracer attached),
- Key metabolites ( $\beta$ -hydroxybutyrate, acetoacetate, lactate, pyruvate, FFA, glycerol), and
- Key hormones (insulin, C-peptide, glucagon).

For each of the lab tests, the following parameters will be derived (as appropriate):

- $AUC_{(0-16)}$ ,
- $AUC_{(0-2)}$ ,  $AUC_{(0-4)}$ ,  $AUC_{(0-8)}$ ,  $AUC_{(0-12)}$ ,
- $AUC_{(2-16)}$ ,  $AUC_{(4-16)}$ ,  $AUC_{(8-16)}$ ,  $AUC_{(12-16)}$ ,
- $C_{max}$  (endogenous glucose production only),
- $T_{max}$  (endogenous glucose production only), and
- $T_{lag}$  (endogenous glucose production only).

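### The primary variable is described as labelled glucose integrated from time 0, but Section 1 derives endogenous glucose production from a tracer ratio that applies from about 3 hours

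*Combined protocol and SAP*

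**What the plan says.** The endpoint and analysis sections treat EGP as a labelled-glucose measurement:

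- The primary endpoint in the Synopsis and Section 2 is "Difference in endogenous glucose production between active and placebo as measured by the glucose with tracer attached", with AUC(0-16) as the parameter. Section 8.3 repeats this as the difference in "endogenous glucose production between active and placebo as measured by the glucose with tracer attached". The primary objective labels the window AUC(0-last).
- Secondary endpoint 6a uses EGP "as measured by the glucose with tracer attached using other parameters including, but not limited to" further AUC intervals, Cmax, Tmax and Tlag.
- Sections 6.2.1 and 8.4.1 list the variable as "Endogenous Glucose Production (glucose that is produced by the liver which has the tracer attached".
- The sampling text (Synopsis design, Sections 3.1, 3.4.1 and 3.5.1) reads "Blood samples will be collected to measure endogenous glucose (tracer attached), plasma glucose, metabolites and hormones". Table 1 has a row for tracer-marked glucose.

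Section 1 describes something else. The tracer, "infused intravenously at a constant rate will equilibrate with endogenous glucose across its distribution space within ~3 hours". After that point, "the ratio of the tracer infusion rate to the plasma tracer/tracee ratio (as assayed by GCMS) measures EGP". The drug effect is expected in the 13 hours that follow.

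Appendix A confirms a constant intravenous infusion of labelled glucose. It gives no EGP formula, priming dose or time limit. Section 8 leaves further detail to a statistical analysis plan, but no such derivation appears in the supplied text.

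**The concern.** There are two faults, and both affect the only primary endpoint.

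The first is what is measured. Labelled glucose comes from the infusion pump, not the liver. Its plasma level is set by how fast it is infused and how fast it is cleared. Section 8.1 defines success as higher EGP on placebo than on ORMD-0801. If the literal wording were programmed, a real fall in EGP at unchanged clearance would be missed, and a rise in clearance alone would look like success.

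The second is the window. If the Section 1 formula is programmed instead, the AUC starts 3 hours before the period in which Section 1 says the formula measures EGP. Someone then has to decide how to treat those hours. Unless this is fixed beforehand, it may be decided with the data in hand. The same gap affects several secondary AUCs and EGP Cmax and Tmax.

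**Working it through.** **The plan's own figures.** 16 h of infusion − about 3 h of equilibration = 13 h, as Section 1 states. The Appendix A example also reproduces: 0.28 × 960 × 90 = 24,192 µmol.

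**Share of each window before 3 h.** Table 2 has 19 times: baseline, 45, 90, 120 and 150 min, then hourly from 3 to 16 h. Five precede 3 h.

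- AUC(0-16): 3/16 = 18.75%
- AUC(0-2): 100%
- AUC(0-4): 3/4 = 75%
- AUC(0-8): 3/8 = 37.5%
- AUC(0-12): 3/12 = 25%
- AUC(2-16): 1/14 = 7.1%
- AUC(4-16), AUC(8-16) and AUC(12-16): 0%

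**Model, for illustration only.** One pool and an unprimed infusion F = 0.28 µmol/kg/min (Appendix A). Assumed, not in the documents: clearance MCR 1.4-1.8 mL/kg/min, volume V 200-250 mL/kg, baseline EGP 12 µmol/kg/min. Unlabelled glucose G follows V·dG/dt = EGP − MCR·G. Labelled glucose g follows V·dg/dt = F − MCR·g, with g(0) = 0. Let k = MCR/V.

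**Literal reading.** EGP does not appear in the equation for g, so at fixed clearance EGP −20% changes labelled AUC(0-16) by 0.0%. The AUC is (F/MCR) × [960 − (1 − e^(−960k))/k].

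- MCR 1.4, V 200: k = 0.007, AUC = 0.2 × (960 − 142.7) = 163.5.
- MCR +20% (1.68): k = 0.0084, AUC = (0.28/1.68) × (960 − 119.0) = 140.2, which is 14.3% lower with EGP unchanged.
- By trapezoid on the 19 times, over the four combinations of MCR and V: −13.6% to −14.9%.
- If clearance rises as glucose falls (MCR proportional to glucose^(−a), a = 0.25-0.5; MCR 1.5, V 225), EGP −20% gives −5.0% to −12.9% when EGP steps down at time 0, and −6.0% to −17.1% at steady state. This response is indirect, through clearance.

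**Section 1 formula.** With constant EGP, the tracer/tracee ratio is (F/EGP)(1 − e^(−kt)). Infusion rate divided by ratio, over true EGP, is therefore 1/(1 − e^(−kt)). At t = 0 the denominator is zero, so the value is undefined.

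| | Assumed MCR and V (k = 0.0056-0.009/min) | k set to match Section 1 (0.0128-0.0217/min) |
|---|---|---|
| Equilibrated at 3 h | 64-80% | 90-98% |
| Overstatement at 45 min | 3.0- to 4.5-fold | 1.6- to 2.3-fold |
| Overstatement at 3 h | 25-57% | 2-11% |
| Mean overstatement, 3-16 h | 3-10% | 0.1-1.1% |

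The right-hand k values are −ln(0.10)/180 and −ln(0.02)/180. The 90-98% range is a reading of the roughly 3-hour equilibration in Section 1.

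**Does the formula track EGP over 3-16 h?** With the assumed MCR and V, EGP −20% shows as −18.1% to −19.4% (step) or −20.0% (steady state). Clearance +20% alone shows as only −0.9% to −3.3%. Before 3 h the formula is dominated by tracer build-up: in every noise-free case run, its maximum fell at 45 min, the first sample after the start.

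**The case against.** The best defence is that the wording is loose shorthand and Section 1 governs. Section 1 names the formula and the assay, Table 2 draws tracer and glucose separately at every time, and Appendix A is an EGP procedure that saves an aliquot of the infusate. Section 8 promises more detail, and Sections 6.2.1 and 8.4.1 let parameters be derived as appropriate. Most of this stands: the sponsor probably intends the Section 1 calculation. It does not close the gap. No endpoint or analysis section refers to that calculation, and the calculation does not cover the first 3 hours of the AUC(0-16) that Section 8.3 names.

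A reader might draw three stronger conclusions that are not supported:

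- *The primary comparison is biased.* Under the Section 1 formula with equal kinetics, the factor 1/(1 − e^(−kt)) is common to both arms and largely cancels.
- *Labelled glucose can never respond to EGP.* That holds at fixed clearance. If clearance depends on glucose, it responds indirectly.
- *Labelled glucose always peaks at 16 h, so its Cmax and Tmax carry no information.* That holds only at constant clearance. With a = 0.5 and a step fall in EGP, the peak came at 6-10 h.

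Section 1 also does not forbid earlier use. It only says from when the ratio measures EGP, and a non-steady-state equation could cover the early hours. None is specified.

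**Conclusion.** The definition is wrong as written and must be corrected before analysis. The core of this needs no model: the text calls infused label liver-produced glucose, and it integrates from time 0 a quantity that its own Section 1 supports from about 3 h. The affected part of the primary window is 18.75% of the time and 5 of 19 samples.

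The size of the error is illustrative and rests on assumed one-pool kinetics: 1.6- to 4.5-fold at 45 min, 2-57% at 3 h, and 0.1-10% on average over 3-16 h. The low ends agree with equilibration by about 3 h. The high ends assume slower kinetics than Section 1 describes, in which case 3 h would itself be somewhat early. What is shown is an undefined primary derivation, not a biased treatment comparison.

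**What to change.** Replace the tracer-attached and tracer-marked wording throughout (Synopsis, Sections 2, 3.1, 3.4.1, 3.5.1, 6.2.1, 8.3, 8.4.1 and Table 1) with: EGP(t) = actual tracer infusion rate per kg / background-corrected plasma tracer/tracee ratio at time t. The actual rate matters because the Appendix A example delivers 4.5 g/500 mL × 0.5 mL/min / 90 kg = 50 µg/kg/min, against the stated 51.

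Then choose one of the following, and use the same window in the primary objective:

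- compute the primary EGP AUC over 3-16 h; or
- keep AUC(0-16) and derive EGP(t) with a pre-specified non-steady-state equation and pool volume.

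Report the method not chosen as a sensitivity analysis. Do not compute EGP AUCs, Cmax or Tmax from the rate/ratio formula on data before 3 h. Define Tlag on EGP(t), or omit it under the existing as-appropriate clause. Metabolite and hormone AUCs are unaffected.

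The cost is wording and programming, since tracer and glucose are already drawn at all 19 times. Each choice has a downside. The 3-16 h window leaves out the first 3 hours after the evening dose, so an effect confined to them would be missed. The non-steady-state route depends on the assumed pool volume early on: in the illustration, a volume wrong by ±20% moved mean EGP over 0-16 h by about ±13%, against about ±2% over 3-16 h.
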